8.3 ADVERSE EVENTS AND SERIOUS ADVERSE EVENTS

8.3.1 DEFINITION OF ADVERSE EVENTS (AE)

Adverse event means any untoward medical occurrence associated with the use of an intervention in humans, whether or not considered intervention-related (21 CFR 312.32 (a)).

8.3.2 DEFINITION OF SERIOUS ADVERSE EVENTS (SAE)

An adverse event (AE) or suspected adverse reaction is considered "serious" if, in the view of either the investigator or sponsor, it results in any of the following outcomes: death, a life-threatening adverse event, inpatient hospitalization or prolongation of existing hospitalization, a persistent or significant incapacity or substantial disruption of the ability to conduct normal life functions, or a congenital anomaly/birth defect. Important medical events that may not result in death, be life-threatening, or require hospitalization may be considered serious when, based upon appropriate medical judgment,

they may jeopardize the participant and may require medical or surgical intervention to prevent one of the outcomes listed in this definition. Examples of such medical events include allergic bronchospasm requiring intensive treatment in an emergency room or at home, blood dyscrasias or convulsions that do not result in inpatient hospitalization, or the development of drug dependency or drug abuse.

8.3.3 CLASSIFICATION OF AN ADVERSE EVENT

8.3.3.1 SEVERITY OF EVENT

For adverse events (AEs) not included in the protocol defined grading system, the following guidelines will be used to describe severity.

- **Mild** – Events require minimal or no treatment and do not interfere with the participant's daily activities.
- **Moderate** – Events result in a low level of inconvenience or concern with the therapeutic measures. Moderate events may cause some interference with functioning.
- **Severe** – Events interrupt a participant's usual daily activity and may require systemic drug therapy or other treatment. Severe events are usually potentially life-threatening or incapacitating. Of note, the term "severe" does not necessarily equate to "serious".

8.3.3.2 RELATIONSHIP TO STUDY INTERVENTION

All adverse events (AEs) must have their relationship to study intervention assessed by the clinician who examines and evaluates the participant based on temporal relationship and his/her clinical judgment. The degree of certainty about causality will be graded using the categories below. In a clinical trial, the study product must always be suspect.

- **Related** – The AE is known to occur with the study intervention, there is a reasonable possibility that the study intervention caused the AE, or there is a temporal relationship between the study intervention and event. Reasonable possibility means that there is evidence to suggest a causal relationship between the study intervention and the AE.
- **Not Related** – There is not a reasonable possibility that the administration of the study intervention caused the event, there is no temporal relationship between the study intervention and event onset, or an alternate etiology has been established.

8.3.3.3 EXPECTEDNESS

The PI will be responsible for determining whether an adverse event (AE) is expected or unexpected. An AE will be considered unexpected if the nature, severity, or frequency of the event is not consistent with the risk information previously described for the study intervention.

8.3.4 TIME PERIOD AND FREQUENCY FOR EVENT ASSESSMENT AND FOLLOW-UP

The occurrence of an adverse event (AE) or serious adverse event (SAE) may come to the attention of study personnel during study visits, during study telephone calls, and interviews of a study participant presenting for medical care.

All AEs including local and systemic reactions not meeting the criteria for SAEs will be captured on the appropriate case report form (CRF). Information to be collected includes event description, time of onset, clinician's assessment of severity, relationship to study product (assessed only by those with the training and authority to make a diagnosis), and time of resolution/stabilization of the event. All AEs occurring while on study must be documented appropriately regardless of relationship. All AEs will be followed to adequate resolution.

Any medical condition that is present at the time that the participant is screened will be considered as baseline and not reported as an AE. However, if the study participant's condition deteriorates at any time during the study, it will be recorded as an AE.

Changes in the severity of an AE will be documented to allow an assessment of the duration of the event at each level of severity to be performed. AEs characterized as intermittent require documentation of onset and duration of each episode.

Study personnel will record all reportable events with start dates occurring any time after informed consent is obtained until 7 (for non-serious AEs) or 30 days (for SAEs) after the last day of study participation. At each study visit, the investigator will inquire about the occurrence of AE/SAEs since the last visit. Events will be followed for outcome information until resolution or stabilization.

8.3.5 ADVERSE EVENT REPORTING

All AEs will be captured and recorded at each stimulation visit in person, and one day after, and four days after each stimulation visit over telephone. The AE report form will be completed by the researcher, and will include details about the stimulation, what is known about previous reported side effects, if the AE occurred in temporal relation to the stimulation, whether the AE improves or completely resolves once stimulation is ceased, whether the AE is worsening of a baseline symptom, and whether the AE is related to concurrent medication or medical condition. This form will be presented to the PI who will review and sign the form. Completed forms will be placed in the participant's file in the study binder. AEs will also be documented in the AE log, which will also document the date, severity, relationship to treatment (as determined by the PI), actions taken, and outcome. Medical conditions and symptoms present prior to start of stimulation on the day of the visit will not be considered an AE.

8.3.6 SERIOUS ADVERSE EVENT REPORTING

The study investigator shall complete an Unanticipated Adverse Device Effect Form and submit to the reviewing Institutional Review Board (IRB) as soon as possible, but in no event later than 10 working days after the investigator first learns of the effect. The study team is responsible for conducting an evaluation of an unanticipated adverse device effect and shall report the results of such evaluation to the Food and Drug Administration (FDA) and the reviewing IRB within 10 working days after they first

receive notice of the effect. Thereafter, the sponsor shall submit such additional reports concerning the effect as FDA requests.

8.3.7 REPORTING EVENTS TO PARTICIPANTS

N/A

8.3.8 EVENTS OF SPECIAL INTEREST

N/A

8.3.9 REPORTING OF PREGNANCY

N/A

8.4 UNANTICIPATED PROBLEMS

8.4.1 DEFINITION OF UNANTICIPATED PROBLEMS (UP)

The Office for Human Research Protections (OHRP) considers unanticipated problems involving risks to participants or others to include, in general, any incident, experience, or outcome that meets all of the following criteria:

- Unexpected in terms of nature, severity, or frequency given (a) the research procedures that are described in the protocol-related documents, such as the Institutional Review Board (IRB)-approved research protocol and informed consent document; and (b) the characteristics of the participant population being studied;
- Related or possibly related to participation in the research (“possibly related” means there is a reasonable possibility that the incident, experience, or outcome may have been caused by the procedures involved in the research); and
- Suggests that the research places participants or others at a greater risk of harm (including physical, psychological, economic, or social harm) than was previously known or recognized.

This definition could include an unanticipated adverse device effect, any serious adverse effect on health or safety or any life-threatening problem or death caused by, or associated with, a device, if that effect, problem, or death was not previously identified in nature, severity, or degree of incidence in the investigational plan or application (including a supplementary plan or application), or any other unanticipated serious problem associated with a device that relates to the rights, safety, or welfare of subjects (21 CFR 812.3(s)).

8.4.2 UNANTICIPATED PROBLEM REPORTING

The investigator will report unanticipated problems (UPs) to the reviewing Institutional Review Board (IRB) and to the principal investigator (PI). The UP report will include the following information:

- Protocol identifying information: protocol title and number, PI's name, and the IRB project number;
- A detailed description of the event, incident, experience, or outcome;
- An explanation of the basis for determining that the event, incident, experience, or outcome represents an UP;
- A description of any changes to the protocol or other corrective actions that have been taken or are proposed in response to the UP.

To satisfy the requirement for prompt reporting, UPs will be reported using the following timeline:

- UPs that are serious adverse events (SAEs) will be reported to the IRB and to the DCC/study sponsor within 10 days of the investigator becoming aware of the event.
- Any other UP will be reported to the IRB within 30 days of the investigator becoming aware of the problem.

8.4.3 REPORTING UNANTICIPATED PROBLEMS TO PARTICIPANTS

N/A

9 STATISTICAL CONSIDERATIONS

Statistical planning and analysis will be done by the PI [name] in collaboration with [name] and consultation with biostatistician [name].

9.1 STATISTICAL HYPOTHESES

Aim 1

H_0 : Mean change in Frontal midline theta power on electroencephalogram after iTBS to the medial prefrontal cortex will be equal to FMT changes after dorsolateral prefrontal cortex stimulation and stimulation of S1.

H_1 : Mean change in Frontal midline theta power on electroencephalogram after iTBS to the medial prefrontal cortex will be greater than FMT changes after dorsolateral prefrontal cortex stimulation and stimulation of S1.

Primary Outcome Measure: The primary objective will test the degree of change in frontal midline theta (FMT) power (μ) before and after iTBS at each stimulation location. The primary outcome measure will be FMT power. *Aim 2a Hypothesis:*

H_0 : There is zero correlation between severity of autonomic dysfunction symptoms at baseline before stimulation with frontal midline theta power at baseline on electroencephalogram.

H_1 : There is a negative correlation between severity of autonomic dysfunction symptoms at baseline before stimulation with frontal midline theta power at baseline on electroencephalogram.

Aim 2b Hypothesis:

H_0 : There is no correlation between severity of depression symptoms at baseline before stimulation with frontal midline theta power on electroencephalogram at baseline.

H_1 : There is negative correlation between depression symptoms at baseline before stimulation with frontal midline theta power on electroencephalogram at baseline.

- Primary Outcome Measures: We will test associations between autonomic symptoms, depression symptoms, and FMT power at baseline before stimulation, where the FMT power (μ) will be the primary outcome measure.

Exploratory objectives

Aim 3 Hypothesis:

H_0 : Change in SCOPA-AUT and OHQ will be zero one day after stimulation and 4 days after stimulation compared to pre-stimulation.

H_1 : Change in SCOPA-AUT and OHQ will be less than zero one day after stimulation and 4 days after stimulation.

- Primary Outcome Measures: Change in SCOPA-AUT and OHQ from before to one day and 4 days after stimulation

Aim 4 Hypothesis:

H_0 : Change in BDI-II will be zero one day after stimulation and 4 days after stimulation compared to pre-stimulation.

H_1 : Change in BDI-II will be less than zero one day after stimulation and 4 days after stimulation.

- Primary Outcome Measure: Change in BDI-II before to one day and 4 days after stimulation

Aim 5 is to maintain a de-identified database of EEG, clinical, and demographic data from people with PD undergoing iTBS.

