H_1 : Change in SCOPA-AUT and OHQ will be less than zero one day after stimulation and 4 days after stimulation.

Aim 4: To evaluate the effect of iTBS on depression symptoms one day after, and 4 days after stimulation.

Hypothesis:

H_0 : Change in BDI-II will be zero one day after stimulation and 4 days after stimulation compared to pre-stimulation.

H_1 : Change in BDI-II will be less than zero one day after stimulation and 4 days after stimulation.

Aim 5: To create a database of EEG and TMS data in people with PD for the purpose of future research into novel neurostimulation therapies for PD NMS.

Hypothesis: We will maintain a de-identified database of EEG, clinical, and demographic data from people with PD undergoing iTBS.

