4.2 SCIENTIFIC RATIONALE FOR STUDY DESIGN

The stimulation locations in the current study design were chosen due to prior data implicating the medial prefrontal cortex and dorsolateral prefrontal cortex in both autonomic and affective disorders. Primary sensory cortex was chosen as a control site due to its limited involvement in Parkinson's disease pathology, autonomic function, and depression. We chose a control stimulation location rather than sham stimulation because participants will be able to feel the difference between real and sham stimulation in this crossover design. A triple crossover design was chosen to maximize study recruitment and minimize subject variability between stimulation arms.

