8 STUDY ASSESSMENTS AND PROCEDURES

8.1 EFFICACY ASSESSMENTS

8.1.1 SELF-COMPLETED QUESTIONNAIRES

Participants will fill out the following questionnaires:

- Scales for Outcomes in Parkinson's – autonomic (SCOPA-AUT) – Autonomic self-completed symptom questionnaire, contains 21 questions plus 2 questions that are specific for men and 2 specific for women; therefore every participant will answer 23 questions⁵². Each item score range is 0-3 for severity of symptoms. Score range is 0-69 points, where higher points

indicates higher burden of symptoms. This will be completed prior to each stimulation session in person, and over telephone one day after and 4 days after stimulation

- Orthostatic Hypotension Questionnaire (OHQ)⁵³ - a validated questionnaire for symptoms of orthostatic intolerance, contains 10 questions. Each question is scored out of 10 possible points. Score range is 0-100, where higher points indicates higher burden of symptoms. This will be completed prior to each stimulation session in person, and over telephone one day after and 4 days after stimulation
- Beck Depression inventory II (BDI-II)⁵⁴ - recommended tool for screening and assessment of depression severity in PD⁵⁵. Consists of 21 questions, each question ranges in score from 0-3 points. Score range is 0-63, where higher points indicates higher burden of symptoms. This will be completed prior to each stimulation session in person, and over telephone one day after and 4 days after stimulation
- MDS - Unified Parkinson's disease Rating Scale (MDS-UPDRS) parts 1b and 2 – Validated clinical tool, it is a rating scale for disease severity in Parkinson's disease. Part 1b is the Non-Motor Aspects of Experiences of Daily Living, and consists of 7 questions, each worth 0-4 points. Score range is 0-28 points. Part 2 is the patient ADL questionnaire and contains 13 questions⁵¹, each worth 0-4 points. Score range is 0- 52 points, This will be completed at the screening visit only.
- Freezing of Gait questionnaire– Assesses symptoms of freezing of gait in Parkinson disease. Contains 6 questions, each scored 0-4⁵⁶. Score range is 0-24, with higher score meaning higher burden of symptoms. This will be completed at the screening visit only
- Epworth sleepiness scale – Assesses symptoms of fatigue and sleepiness. Contains 8 questions, each scored 0-4.⁵⁷ Score range is 0-24, with higher score meaning higher burden of symptoms. This will be completed at the screening visit only.

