9.4 STATISTICAL ANALYSES

9.4.1 GENERAL APPROACH

All data are double entered by independent keyboard operators, compared to identify discrepancies, then reconciled with the data manager. All datasets are backed up daily. Linear mixed models with repeated measures across different regions or over time will be the primary analytic tool for testing our *a priori* hypotheses. To model correlation among repeated measures, we will primarily consider either random intercept or AR(1). We will use the likelihood ratio test (or Wald test) statistic to test

the hypotheses. We will appropriately handle missing data (e.g., missing responses and/or covariates) by using imputation or other methods. To identify significant component terms in each of the models, we will examine the parameter estimates, 95% confidence intervals, and p-values of the component terms in an analysis of fixed effects for the final mixed models. Before undertaking statistical modeling, we will perform descriptive analyses and examine the distributions of all measures. Appropriate transformations or nonparametric statistical tests will be considered if necessary. **All statistical estimates of population parameters will be tabulated along with corresponding confidence intervals (CIs) and/or standard errors (SEs) to convey levels of precision / imprecision.** Following is a detailed plan for testing each hypothesis and the power assessment when feasible.

Descriptive statistics: Categorical data (sex) will be presented as percentages. Continuous data (age, disease duration, scores on SCOPA-AUT, OHQ, BDI-II, MDS-UPDRS all parts, freezing of gait questionnaire, Epworth Sleepiness scale, REM sleep behavior disorder questionnaire, and MoCA, will be presented as means with standard deviation and range.

Primary analysis, Aim 1: To test the degree of change in the power of FMT before and after iTBS at each location, we will use linear mixed models with FMT being the dependent variable. We will primarily include stimulation location (mPFC, DLPFC, S1), time (before, after stimulation), and the interaction term Location*time in the model.

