Primary Analysis, Aim 2: 1. To test associations of autonomic symptoms in PD subjects with FMT, we will use linear regression modeling. The dependent variable will be FMT, whereas primary covariates will be SCOPA-AUT, OHQ score, and magnitude of systolic blood pressure reduction during orthostatic blood pressure measurement. We will further use linear regression models to examine the associations between depression symptoms in PD subjects and FMT, using linear regression modeling. **Exploratory Analyses:** 1. We will use linear mixed models to examine the effect of iTBS on autonomic symptoms one day after, and 4 days after stimulation. SCOPA-AUT and OHQ will be the dependent variable in the ANOVA analysis. The factors will be stimulation location (mPFC, DLPFC, S1) by time (before and after). 2. Similarly, we will use linear mixed models to evaluate the effect of iTBS on depression symptoms one day after, and 4 days after stimulation. BDI-II will be the dependent variable, whereas the primary factors will be stimulation location (mPFC, DLPFC, S1) by time (before and after). **In all statistical models,** Some key confounding factors (age, disease duration) will be controlled in both linear mixed effects and regression models. **Post-hoc analysis** will be performed using Tukey's method to control for multiple comparisons.

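### Exploratory Aims 3 and 4 are worded as before-after change with no site and no S1 comparison, and no term of the location-by-time model is named as deciding them

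*Combined protocol and SAP*

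**What the plan says.** Aims 3 and 4 are stated in sections 4.1, 9.1 and 9.2, each time in the same form. For Aim 3 the null is "Change in SCOPA-AUT and OHQ will be zero one day after stimulation and 4 days after stimulation compared to pre-stimulation" and the alternative is "Change in SCOPA-AUT and OHQ will be less than zero one day after stimulation and 4 days after stimulation". For Aim 4 the null is "Change in BDI-II will be zero one day after stimulation and 4 days after stimulation compared to pre-stimulation", again with a fall as the alternative. None of these statements mentions a stimulation site.

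Aim 1 is handled differently. Its alternative in section 9.1 is that the mPFC change "will be greater than FMT changes after dorsolateral prefrontal cortex stimulation and stimulation of S1", and its model in section 9.4.1 includes location, time "and the interaction term Location*time in the model".

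For Aim 3, section 9.4.1 plans a linear mixed model: "The factors will be stimulation location (mPFC, DLPFC, S1) by time (before and after". Aim 4 has the same factors with BDI-II as the outcome. The same section presents mixed models as the main tool for the a priori hypotheses, tested by likelihood ratio or Wald statistics and reported with 95% confidence intervals. It adds Tukey-adjusted post-hoc comparisons for all models.

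On the control, section 4.2 says: "We chose a control stimulation location rather than sham stimulation". On data collection, section 8.1.1 has SCOPA-AUT, OHQ and BDI-II completed "prior to each stimulation session in person, and over telephone one day after" and again by telephone four days after.

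**The concern.** The hypotheses and the model ask different questions. The hypotheses ask whether scores fall after stimulation. The model can also ask whether they fall more after mPFC or DLPFC than after S1, which is the question the control site was brought in to answer. The plan does not say which of the two decides Aims 3 and 4, so two analysts, one working from 9.1 and one from 9.4.1, could report opposite conclusions from the same data.

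An uncontrolled fall has several possible sources here. Participants may expect benefit, the same questionnaires are repeated within days, and every pre-stimulation score is taken in person while every post-stimulation score is taken by telephone. These act at all three sites. Under the hypotheses as written, S1 itself could be counted as effective.

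The aims are exploratory in a pilot. They are, however, the only planned analyses of whether symptoms change after stimulation, and section 2.1 gives the overarching objective as the feasibility of treating autonomic dysfunction and depression with TMS.

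**Working it through.** **1. The plan's own figure.** Section 9.2 gives power 0.95 (0.26 to 1.00) for Aims 3 and 4, from N=45, alpha 0.05, two predictors and g = 1.0 (0.3 to 1.7). Take f² = g²/4, noncentrality √(f²·N) and 45 − 2 − 1 = 42 degrees of freedom. At g = 1.0, f² = 0.25 and the noncentrality is √11.25 = 3.354.

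| g | One coefficient, one-sided 5% | One coefficient, two-sided 5% |
|---|---|---|
| 0.3 | 0.256 | 0.166 |
| 1.0 | 0.951 | 0.906 |
| 1.7 | 1.000 | 1.000 |

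The stated figure reproduces as a one-sided test of one coefficient and is not arithmetically wrong. The two predictors are not named, so the figure does not show which effect was powered.

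**2. Which model term answers which hypothesis.** Let δ(mPFC), δ(DLPFC) and δ(S1) be the mean changes from pre-stimulation.

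- The hypothesis as written is δ = 0 against δ < 0. In a location-by-time model this is the time effect. Depending on coding, it is the change at one reference site or the average over the three.
- The controlled question is δ(mPFC) − δ(S1) = 0, and likewise for DLPFC. This is a location*time contrast.

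If all three changes equal the same non-zero value, the first null is false and the second is true.

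**3. Size, by illustration.** N=48 is from section 9.2. The documents give neither the SD of change nor the correlation between changes at different visits (ρ). I assume a shared fall of d = 0.2 or 0.3 SD of change and ρ = 0, 0.3 or 0.5. The test is a one-sample noncentral t with 47 degrees of freedom.

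- One site: noncentrality d√48. For d = 0.3 this is 2.078.
- Pooled over three sites: standardised change d/√((1+2ρ)/3). For d = 0.3 this is 0.520, 0.411 and 0.367 at ρ = 0, 0.3 and 0.5.
- mPFC minus S1: true value 0 in every case.

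Probability of rejection under a shared fall:

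| Test | d = 0.3, two-sided | d = 0.3, one-sided | d = 0.2, two-sided | d = 0.2, one-sided |
|---|---|---|---|---|
| One site, S1 included | 0.53 | 0.66 | 0.27 | 0.39 |
| Pooled, ρ = 0 | 0.94 | 0.97 | 0.65 | 0.76 |
| Pooled, ρ = 0.3 | 0.80 | 0.88 | 0.46 | 0.59 |
| Pooled, ρ = 0.5 | 0.70 | 0.81 | 0.38 | 0.51 |
| mPFC minus S1 | about 0.05 | about 0.05 | about 0.05 | about 0.05 |

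The last row was confirmed by simulation with 20,000 trials per setting (0.048 to 0.053 one-sided, about 0.05 two-sided).

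**4. Precision of the controlled contrast.** Its standard error is √(2(1−ρ)) times that of the change at one site: 1.41, 1.18 and 1.00 at ρ = 0, 0.3 and 0.5. At N=48 and 80% power the detectable one-site change is 0.413 SD two-sided. The detectable mPFC-minus-S1 difference is therefore 0.58, 0.49 and 0.41 SD of change (0.52, 0.43 and 0.36 one-sided).

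**The case against.** **The plan already has the comparison.** A reader might infer that the plan never compares sites for symptoms, or never ties the model to these hypotheses. The documents do not support that. Section 9.4.1 makes mixed models the tool for the a priori hypotheses, the entry for Aims 3 and 4 is location by time, and Tukey comparisons follow. Location by time would ordinarily be read as including the interaction, and a shared fall should be visible in the estimates. What stands is narrower: the deciding term is named for Aim 1 but not for Aims 3 and 4, and their written hypothesis corresponds to the time effect.

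**One-sided testing is not stated.** The alternatives are directional, so a reader might infer one-sided tests. Section 9.4.1 does not say so, Aims 1 and 2 are also worded directionally, and the one-sided match in section 9.2 is an inference. Both sets of rejection rates are given for that reason; the point holds on either.

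**A shared fall need not be a false conclusion.** S1 receives active iTBS, and the stated aim is the effect of iTBS on symptoms. An improvement at all sites could be real, and the contrast with S1 would not detect it. This is right. The before-after test cannot distinguish that possibility from a non-specific response, however, and section 4.2 chose S1 for its limited involvement in autonomic function and depression, which favours the contrast.

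**The numbers are illustrative.** Nothing in the documents shows that a shared fall will occur or how large it would be. That also stands.

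**Conclusion.** The point holds as a mismatch between hypothesis and analysis in two exploratory aims. As worded, Aims 3 and 4 would be met by a fall common to all sites, S1 included, and that result could not be attributed to the stimulated target. With an assumed shared fall of 0.3 SD of change, the null is rejected with probability 0.53 two-sided (0.66 one-sided) at one site. Pooled, the figure is 0.70 to 0.94 two-sided (0.81 to 0.97 one-sided) for ρ from 0.5 down to 0. The mPFC-minus-S1 contrast rejects at about 0.05. These figures rest on assumed effects and correlations and say nothing about how likely a shared fall is.

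It does not follow that the plan lacks a site comparison, that one-sided tests are specified, or that a shared fall would be spurious. The power arithmetic in section 9.2 is not at fault, and Aims 1 and 2 are unaffected. The correction is worth making because it is nearly free.

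**What to change.** - **Sections 4.1, 9.1 and 9.2.** Restate the null and alternative for Aims 3 and 4 as change at mPFC minus change at S1, and change at DLPFC minus change at S1, at day 1 and at day 4.
- **Section 9.4.1.** Name these location*time contrasts as the deciding test for Aims 3 and 4. Code time as pre, +1 day and +4 days, so that the model matches the two time points in the hypotheses.
- **Reporting.** Give within-site and pooled change descriptively with confidence intervals, and state that they are not evidence of a site-specific effect. This keeps an improvement common to all sites in view.

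The cost is a rewording of the hypotheses and a sentence or two in 9.4.1; the visits, questionnaires and model are already planned. There are two statistical costs. When ρ is below 0.5 the contrast is less precise than the change at one site, with a detectable difference of about 0.58, 0.49 or 0.41 SD of change at ρ = 0, 0.3 or 0.5 (80% power, two-sided). It also cannot detect an effect of iTBS that is the same at every site. If the investigators want that question answered as well, they should state it separately and acknowledge that this design has no sham arm to control it. The aims should stay exploratory.
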